**CONFIDENTIALITY**

Prevention of disclosure, to other than authorized individuals, of a Sponsor's proprietary information or of a subject's identity / Protected Health Information (PHI) in compliance with the Health Insurance Portability and Accountability Act of 1996 (HIPAA).

**DEVICE FAILURE / MALFUNCTION**

The failure of a device to meet its performance specifications or otherwise perform as intended. Performance specifications include all claims made in the labeling for the device. The intended performance of a device refers to the intended use for which the device is labeled or marketed.

**DEVICE SUCCESS**

Defined as the ability to deploy the delivery system, deliver the collagen, and achieve hemostasis with the Cardiva VASCADE™ Vascular Closure System alone or with adjunctive compression.

**ELECTRONIC CASE REPORT FORM (eCRF)**

An electronic document designed to record all of the protocol-required information to be reported to the Sponsor on each subject.

**EMBOLISM**

The sudden blocking of an artery by a clot or other material that has been brought to its site of lodgment by the blood current (embolus). Potential sources of emboli include blood clots, fat globules, air bubbles, tissue, clumps of bacteria, thrombus or foreign material.

**EMBOLIZATION OF DEVICE COMPONENTS**

Accidental deployment or dislodgement of any component of the Cardiva VASCADE™ VCS into the bloodstream.

**HEMATOMA**

A localized collection of extravasated blood in subcutaneous tissue, usually clotted. A metric ruler should be used to measure the widest portion of the hematoma.

**HEMOSTASIS**

Cessation of common femoral artery bleeding (excluding cutaneous or subcutaneous oozing).

**INDEPENDENT PHYSICIAN ADJUDICATOR (IPA)**

An independent physician, qualified by training and experience in the field of interventional cardiology or radiology, who will review and adjudicate all reported adverse events that are both serious and device-related; and all reported major and minor access site closure-related complications. The IPA is not a participant in the trial and is independent of Cardiva Medical.

**INFLAMMATION**

A localized protective response elicited by injury or destruction of tissues, not necessarily synonymous with infection.

**INFORMED CONSENT**

A process by which a subject voluntarily confirms in writing his or her willingness to participate in a particular investigation, after having been informed of all aspects of the investigation that are relevant to the subject's decision to participate. Informed consent is documented by means of a written, signed, and dated Informed Consent form.

**INTERNATIONAL NORMALIZED RATIO (INR)**

A comparative rating of Prothrombin time (PT) ratios. Used to measure coumadin efficacy in subjects.

**INTIMAL TEAR / DISSECTION**

Disruption of an arterial wall resulting in splitting and separation of the intimal (subintimal) layers.

**INVESTIGATIONAL SITE**

The location(s) where registry-related activities are actually conducted.

**INVESTIGATOR**

The person responsible for the conduct of the registry at a clinical site. The responsible leader of the team and may be called the Principal Investigator. See also Co-Investigator.

**IPSILATERAL**

Situated on or affecting the same side (e.g., same side of the body as the access site).

**IPSILATERAL DEEP VEIN THROMBOSIS**

Presence of a thrombus in the peripheral venous system of the ipsilateral limb. May be a complication of phlebitis or may result from injury to a vein or from prolonged bed rest. Symptoms include a feeling of heaviness, pain, warmth, or swelling in the affected part; diagnosis should be confirmed by ultrasound imaging.

**IPSILATERAL LOWER EXTREMITY ARTERIAL EMBOLI**

Presence of emboli in the peripheral arterial system of the ipsilateral limb; diagnosis should be confirmed by angiographic or ultrasound imaging.

**LATE ACCESS SITE-RELATED ARTERIAL BLEEDING REQUIRING INTERVENTION** (i.e., following hospital discharge) Re-bleeding from the puncture site following hospital discharge and up to 30 days post procedure that requires manual compression or other intervention to prevent a life-threatening event.

**LIFE-THREATENING ADVERSE EVENT**

A device-related injury in which the patient was at substantial risk of dying at the time of the adverse event, or use or continued use of the device might have resulted in the death of the patient.

**LOCALIZED ACCESS SITE INFECTION**

Infection occurring at the access site requiring treatment with oral or intramuscular antibiotic therapy. Does not include administration of prophylactic antibiotic regimens.

**MANUAL COMPRESSION**

Direct digital non-occlusive pressure to the arteriotomy site applied to achieve hemostasis. Note: C-clamp, FemoStop®, Sandbags and other methods are to be used only following the achievement of hemostasis for management of non-arterial oozing/bleeding.

**MEDICAL DEVICE REPORTING REQUIREMENTS (MDR)**

21 CFR 803 Medical Device Reporting are the regulations that establish requirements for medical device reporting for device user facilities (i.e., hospital), manufacturers, importers and distributors regarding incidents where applicable commercially available devices may have caused or contributed to serious injury and death, and/or when the device malfunctions. The following definitions relate to 21 CFR 803 MDR requirements, also see Section 13:

**Caused or contributed:**

Means that a death or serious injury was or may have been attributed to a medical device, or that a medical device was or may have been a factor in a death or serious injury, including events occurring as a result of failure, malfunction, improper or inadequate design, manufacture, labeling, or user error.

Malfunction:

Means the failure of a device to meet any of its performance specifications or otherwise to perform as intended. Performance specifications include all claims made in the labeling of the device. The intended performance of a device refers to the intended use for which the device is labeled or marketed through means such as labeling claims, advertising matter, and oral or written statements of Cardiva representatives.

Medical Device Report (MDR):

Means a report mandated by the FDA to be completed on FDA Form 3500A regarding a reportable event.

MDR Reportable Event:

Any incident about which a Cardiva Medical employee receives or becomes aware of information that reasonably suggests that a Cardiva Medical device; (1) may have caused or contributed to a death or serious injury; or (2) has malfunctioned and that the device or a similar device marketed by Cardiva Medical would likely cause or contribute to a death or serious injury if the malfunction were to recur.

Permanent:

Means irreversible impairment or damage to a body structure or function excluding trivial impairment or damage.

Reasonably Suggests:

Means that a "reasonable" person considering the information would conclude that a reportable event has occurred. Information which leads a person qualified to make a medical judgment (e.g. a physician, nurse, risk manager, clinical engineer, etc.) to reach a reasonable conclusion that a device-related event is or is not reportable is to be documented in the MDR event files.

Serious illness or injury:

Means an injury or illness that (1) is life-threatening; (2) results in permanent impairment of a body function or permanent damage to body structure; or (3) necessitates medical or surgical intervention to preclude permanent impairment of a body function or permanent damage to a body structure. Incidences requiring surgery to remove a malfunctioned device will be considered a serious injury. Retrieval of a fracture piece from a body cavity without the need for additional medical intervention will not be considered a serious injury.

## NEW IPSILATERAL LOWER EXTREMITY ISCHEMIA

New (acute) onset of compromised peripheral blood flow, causing a threat to the viability of the limb and requiring surgical or percutaneous intervention. This compromised blood flow is documented by subject symptoms, physical exam and/or a decreased or absent blood flow on lower extremity angiogram.

#### NEW ONSET ACCESS SITE CLOSURE-RELATED NEUROPATHY IN THE IPSILATERAL LOWER EXTREMITY REQUIRING SURGICAL REPAIR

New onset access site closure-related nerve injury that requires surgical intervention to mitigate symptoms or prevent permanent nerve damage.

#### NEW ONSET ACCESS SITE CLOSURE-RELATED NEUROPATHY IN THE IPSILATERAL LOWER EXTREMITY NOT REQUIRING SURGICAL REPAIR

New onset access site closure-related nerve injury that does not require surgical intervention to mitigate symptoms or prevent permanent nerve damage, however is evaluated to be moderate to severe in nature by the Investigator (see "Adverse Event Severity Rating").

#### OOZING

Minimal bleeding of a cutaneous or subcutaneous origin characterized by the absence of pulsatile arterial flow and controlled with the application of light compression methods (sand bags, pressure dressings, and light manual pressure). Note: the occurrence of oozing will not be incorporated into the "time to hemostasis" measurement.

#### PERFORATION OF VESSEL WALL

A hole or break in the arterial wall (e.g., from insertion of a percutaneous device).

#### PERIPHERAL PULSE ASSESSMENT SCALE

0 = absent; not palpable; 1 = diminished; 2 = expected; 3 = full, increased; 4 = bounding.

#### PERIPHERAL VASCULAR DISEASE

Damage to or dysfunction of the arteries outside the heart resulting in reduced blood flow; *especially*: narrowing or obstruction (as from atherosclerosis) of an artery (as the iliac artery or femoral artery) supplying the legs that is marked chiefly by intermittent claudication and by numbness and tingling in the legs.

#### PERMANENT ACCESS SITE CLOSURE-RELATED NERVE INJURY (> 30 DAYS)

New onset access site closure-related nerve injury that persists for > 30 consecutive days following device removal and is evaluated to be moderate to severe in nature by the Investigator (see "Adverse Event Severity Rating").

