## Protocol Synopsis

### ANTEGRADE-PVD Post-Market Registry Protocol

**A MULTI-CENTER, PROSPECTIVE, POST-MARKET REGISTRY TO EVALUATE PROCEDURAL OUTCOMES DATA USING THE CARDIVA VASCADE™ VASCULAR CLOSURE SYSTEM (VCS) FOR THE MANAGEMENT OF THE FEMORAL ARTERIOTOMY AFTER PERCUTANEOUS ENDOVASCULAR PROCEDURES VIA ANTEGRADE ACCESS**

Primary Objective	
The objective of the ANTEGRADE-PVD registry is to collect procedural outcomes data when the Cardiva VASCADE™ Vascular Closure System (VCS) is used to seal femoral arterial access sites at the completion of ipsilateral peripheral interventional procedures performed through 5-7 Fr introducer sheaths via an antegrade approach.
 
Antegrade access is experiencing growing adoption in catheter-based procedures to treat peripheral artery disease, with many advantages for lower limb procedures in particular. This post-market registry is designed to capture data specific to this procedural technique, and is being conducted under an FDA-approved indication for use for this device.

Device	The Cardiva VASCADE™ Vascular Closure System (VCS) is an FDA-approved device (PMA P120016).
Approved Indication for Use	The Cardiva VASCADE™ Vascular Closure System (VCS) is indicated for femoral arterial access site closure while reducing times to hemostasis and ambulation in patients who have undergone diagnostic or interventional endovascular catheterization procedures utilizing a 5 Fr, 6 Fr or 7 Fr procedural sheath.
Study Design	A multi-center, prospective, single arm post-market registry
Number of Subjects	Up to 100 prospectively enrolled subjects
Number of Sites	Investigators experienced in antegrade access closure w/VASCADE VCS will enroll subjects at up to 7 U.S. sites
Study Duration	It is anticipated that enrollment will commence in December 2016, with final enrollment and 30 day follow-ups completed in Q3 2017. The registry will be considered complete after all enrolled subjects have completed the registry follow-up requirements.

Follow-up Schedule	Each enrolled subject will be followed for up to 30 +/-7 days post-procedure. There will be an office visit between 1-15 days; and a subsequent telephone follow-up will be done between 23-37 days as the final contact.

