Primary Procedural Outcome – Performance	
 
• Time to hemostasis (TTH), defined as elapsed time between device removal and first observed and confirmed arterial hemostasis.
 

Secondary Procedural Outcomes - Performance	
 
• Time to ambulation (TTA), defined as elapsed time between device removal and when subject first stands and walks 20 feet without evidence of arterial re-bleeding from the access site.
 
• Time to hospital discharge (TTD), defined as elapsed time between device removal and when subject is actually discharged from the facility.
 
• Device Success, defined as the ability to deploy the delivery system, deliver the collagen, and achieve hemostasis with the Cardiva VASCADE™ VCS alone or with adjunctive compression
 
• Procedure Success, defined as attainment of Device Success and freedom from major access site closure-related complications through 30 days
 

Primary Procedural Outcomes - Complications	
Patient incidence rate of combined major access site closure-related complications through 30 days:
 
 
• Access site closure-related bleeding requiring transfusion;
 
• Vascular injury requiring repair (via surgery, ultrasound guided compression, transcatheter embolization or stent graft);
 
• New ipsilateral lower extremity ischemia causing a threat to the viability of the limb and requiring surgical or additional percutaneous intervention;
 
• Access site-related infection requiring intravenous antibiotics and/or extended hospitalization;
 
• New onset neuropathy in the ipsilateral lower extremity requiring surgical repair
 
• New onset permanent nerve injury in the ipsilateral lower extremity (> 30 days)
 

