## **4. Study Design**

### **4.1. Overview**

The ANTEGRADE-PVD registry is a multi-center, single arm post-market registry to evaluate procedural outcomes in subjects when the Cardiva VASCADE™ Vascular Closure System (VCS) is used to seal femoral arterial access sites at the completion of ipsilateral peripheral interventional procedures performed through 5-7 F introducer sheaths via an antegrade approach.

Procedural outcomes related to performance and complications will be assessed through hospital discharge and 30 (+/- 7) days post-procedure.

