#### 7.5. Follow-up

All enrolled subjects are required to complete an office visit between days 1-15, and a 30 (+/- 7) day telephone follow-up. Depending on each institution's

standard practice for follow-up visits, subjects may return to the office for access site assessment any time between 1 and 15 days post-procedure. The subject should be instructed that a follow-up telephone assessment will be conducted between day 23 and 37 to complete the study. It is important that all subjects are contacted within the 30 (+/- 7) day window to determine Procedural Success.

During both the office visit and telephone follow-up, the subject should be queried regarding any complications they experienced after hospital discharge and the status of the access site wound should be assessed. All subjects will be evaluated for symptoms of lower extremity neuropathy in the ipsilateral limb that were not existing prior to the index procedure (i.e., paresthesias, numbness, weakness), including an assessment of severity.

In the event of refusal to return to the clinic, a protocol deviation will be reported and a telephone follow-up will be completed.

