### **8.2. Secondary Procedural Outcomes - Performance**

Time to ambulation (TTA) is defined as elapsed time between device removal and when subject first stands and walks 20 feet without evidence of arterial re-bleeding from the access site. The time to ambulation will be measured in hour (hh):minutes (mm). (TTA = T7 – T5).

Time to discharge (TTD) is defined as elapsed time between device removal and when subject is actually discharged from the facility. The time to ambulation will be measured in hour (hh):minutes (mm). (TTA = T8 – T5).

Device Success is defined as the ability to deploy the delivery system, deliver the collagen, and achieve hemostasis with the Cardiva VASCADE™ VCS alone or with adjunctive compression.

Procedure Success is defined as attainment of Device Success and freedom from major access site closure-related complications through 30 days.

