### **8.3. Primary Procedural Outcomes - Complications**

The primary procedural complication composite to be evaluated is the 30-day patient incidence rate of combined major access site closure-related complications. Major complications include:

- Access site closure-related bleeding requiring transfusion;
- Vascular injury requiring repair (via surgery, ultrasound guided compression, transcatheter embolization or stent graft);
- New ipsilateral lower extremity ischemia causing a threat to the viability of the limb and requiring surgical or additional percutaneous intervention;
- Access site-related infection requiring intravenous antibiotics and/or extended hospitalization;
- New onset neuropathy in the ipsilateral lower extremity requiring surgical repair;
- New onset permanent nerve injury in the ipsilateral lower extremity. (> 30 days).

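### Permanent nerve injury (more than 30 days), part of the primary major composite, cannot be judged at a final call on days 23-30, and no later recheck is set

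*Combined protocol and SAP*

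**What the plan says.** **The component.** Section 8.3 lists "New onset permanent nerve injury in the ipsilateral lower extremity", marked as lasting more than 30 days, among the major complications. Section 18.2 defines it as "New onset access site closure-related nerve injury that persists for > 30 consecutive days following device removal" and adds that the Investigator must rate it moderate to severe.

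**The neighbouring minor category.** Section 8.4 lists new neuropathy that does not need surgical repair. Its Section 18.2 definition has no duration limit and sets the same severity threshold: the injury needs no surgery, "however is evaluated to be moderate to severe in nature by the Investigator".

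**The last contact.** The Synopsis (Follow-up Schedule) says "a subsequent telephone follow-up will be done between 23-37 days as the final contact". Section 7.5 says "a follow-up telephone assessment will be conducted between day 23 and 37 to complete the study".

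**The horizon.** The Synopsis gives the primary complication outcome as "Patient incidence rate of combined major access site closure-related complications through 30 days". Section 8.2 defines Procedure Success as Device Success plus "freedom from major access site closure-related complications through 30 days". Section 4.1 says "Procedural outcomes related to performance and complications will be assessed through hospital discharge and 30 (+/- 7) days post-procedure".

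**Related provisions.**
- Sections 7.4.4 and 7.5 have new ipsilateral neuropathy and its severity assessed at discharge, at the office visit and at the call.
- Section 7.6 lets a subject exit only if no condition needs further follow-up.
- Section 13.3 monitors required adverse events until exit and allows medical records to be requested.
- An independent physician adjudicates all reported major and minor closure-related complications (Synopsis, Section 18.2).

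**The concern.** A compliant site can close a subject's follow-up before one component of the primary complication outcome can be observed. A subject with a closure-related, moderate-to-severe neuropathy still present at a call on day 25 has not yet met the major definition but already meets the minor one. No section sets a day for looking again or says how the case is classed if it persists.

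At stake are the class of the event and therefore two reported rates: the major composite and Procedure Success. The event itself is not lost, because it remains reportable as a minor complication.

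**Working it through.** The plan has no figure to reproduce here. Section 9.3 says the sample size was not derived for comparisons, and no threshold is set. The check is a day count, followed by the weight of one case.

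**1. Day count from device removal (day 0)**
- Persistence for more than 30 days: first whole day on which it can be met = 31 (Section 18.2).
- Permitted call days: 23 to 37, so 37 - 23 + 1 = 15 (Synopsis, Section 7.5).
- Too early: days 23 to 30, so 30 - 23 + 1 = 8 of 15.
- Late enough: days 31 to 37, so 7 of 15.
- If elapsed hours are counted (30 x 24 = 720) and the call is late on day 30, only days 23 to 29 are too early: 7 of 15.

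**2. Symptoms that begin after device removal**

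The definition does not make clear whether a later-onset injury needs 30 days from removal or 30 days of symptoms. If the count runs from onset on day k, the earliest day is k + 31.
- Onset on day 1: day 32 is needed, so 9 of 15 call days are too early.
- Onset on day 6: day 37 is needed, the last day of the window.
- Onset on day 7 or later: day 38 or later is needed, so all 15 are too early.

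**3. Where an unresolved case falls at a call on days 23-30**

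| Criterion | Major: permanent injury | Minor: no surgical repair |
|---|---|---|
| New onset, closure-related | met | met |
| Moderate to severe | met | met |
| More than 30 days | cannot yet be met | not required |

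**4. Weight of one case**

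Section 9.2.3.1 specifies 95% Wilson intervals. With z = 1.96 and estimate x/n = p, the limits are [p + z²/(2n) ± z√(p(1-p)/n + z²/(4n²))] / (1 + z²/n). For x = 0 the upper limit reduces to z²/(n + z²), so 0/100 gives 3.84/103.84 = 3.70%.

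| Result at n = 100 | Estimate | 95% Wilson interval |
|---|---|---|
| Major, case classed minor | 0% | 0-3.70% |
| Major, case classed major | 1% | 0.18-5.45% |
| Procedure Success, case classed minor | 100% | 96.30-100% |
| Procedure Success, case classed major | 99% | 94.55-99.82% |

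The table assumes that there is no other major event and that all subjects otherwise succeed.

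**5. How often to expect a case**

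The Instructions for Use (Attachment 2) report permanent nerve injury in 0/275 VASCADE subjects in RESPECT (Wilson upper limit 3.84/278.84 = 1.38%) and 0/30 in the 5F study (3.84/33.84 = 11.35%). Two cautions apply. The attachment gives both studies the same 30 ± 7 day endpoint window, so their zeros may share this limit. RESPECT also excluded clinically significant peripheral vascular disease.

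**The case against.** **The safeguards are real.** A moderate-to-severe neuropathy is, by the protocol's own severity scale, one that interferes with usual activity or needs treatment. That makes it an obvious candidate for continued follow-up under Section 7.6. Section 13.3 lets the sponsor request progress notes, which may document the symptom after day 30, and the adjudicator would see the case. This stands as a narrowing of the gap. It does not close it, because none of these provisions sets a recheck day, and an adjudicator cannot use an observation that nobody made.

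**The 30-day wording.** A reader might infer that findings on days 31-37 do not count, so that this component could never be scored. The documents do not support that reading. Section 4.1 assesses outcomes through the 30 (+/- 7) day window, and Section 7.5 requires contact within that window in order to determine Procedure Success. The Synopsis and Sections 8.2 and 8.3 need only a clarifying line.

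**Certain one-way bias.** A reader might also infer that the error always favours the device. No section says that an unresolved case defaults to minor, and a site or the adjudicator might class it as major before persistence is shown. Understatement follows only under the conditions stated in the verdict.

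**A 53% chance of misclassification.** The ratio 8/15 is a share of permitted days. It becomes a probability only if calls are spread evenly over the window, and the documents give no call dates.

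**The structure is inherited.** The same component and window appear in RESPECT, and Section 1.1 aims for consistency with that trial. This is a reason to disclose a targeted recheck in any comparison. It does not justify leaving the component unobservable on 8 of 15 days.

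**Conclusion.** The point holds and is worth correcting, with a small expected effect. On days 23-30 a compliant final call cannot establish this component of the primary composite, and no recheck is scheduled.

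The major rate is understated and Procedure Success overstated only if four things coincide: a true qualifying injury occurs, the last contact comes before day 31, the Section 18.2 definition is applied strictly, and the subject is neither held under Section 7.6 nor documented in later records obtained under Section 13.3. The documents do not allow the chance of this to be estimated.

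One such case among 100 subjects changes each rate by one percentage point, with overlapping intervals. The registry is descriptive (Sections 9.2.1 and 9.3), so no test or decision rule is affected. The count of 8 days takes device removal as day 0 and uses whole days; it is 7 by elapsed hours with a late call on day 30.

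**What to change.** 1. **Sections 7.5 and 7.6.** For any subject whose new ipsilateral neuropathy is unresolved at the last contact before day 31, make or repeat the final call on days 31-37, before exit. This stays inside the existing window.
2. **Sections 8.3 and 9.2.3.1.** State that observations on days 31-37 count for this component and that the case is scored as major if the Section 18.2 definition is then met. State also whether, for symptoms that begin later, the 30 days still run from device removal. If they run from onset, a recheck by day 37 is enough only for onset up to day 6, and the text should say how later onset is handled. Add one line to the Synopsis and Section 8.2 tying the 30-day wording to the 30 (+/- 7) day window.
3. **Reporting.** Give the number of subjects with unresolved new neuropathy and no contact after day 30. This is a count and leaves the no-imputation rule in Section 9.1.3 untouched.

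**Cost.** Protocol wording and an occasional extra telephone call. The major rate may look slightly less favourable. Ascertainment would be slightly more complete than in the RESPECT follow-up described in the Instructions for Use, which mentions no such recheck; any comparison with RESPECT should say so.
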